11.5.3 Time to Extubation

Descriptive statistics for time to extubation will be presented by treatment group. Time to extubation is defined as the time (hours) from the date/time of intubation to the date/time of extubation.

11.5.4 Physical Examination

Physical examination will be performed at screening, Day 30, Day 360 and at early discontinuation visits. All findings at the screening visit will be recorded on the medical history eCRF page. Any new or worsening condition observed after study injection will be recorded on the adverse event eCRF page. Hence summaries for physical examinations will be captured in summaries presented for medical history and adverse events.

12.0 Interim Analysis

An interim analysis of all efficacy data will be performed when all randomized participants have completed the Day 60 visit or exited the study earlier. The purpose of this analysis is to identify early trends in the data for administrative planning of following studies. There is no plan to stop the study or drop a treatment arm based on the results from the interim analysis. The interim analysis will serve as the primary analysis for the study.

Specifications of tables, figures, and data listings to be generated during the interim analysis are provided in a separate document. On completion of the database lock for the interim/primary analysis, the study will be unblinded to AbbVie study personnel. However, investigators and study sites personnel will remain blinded until completion of the final analysis. The final analysis will occur when all participants have completed the long-term safety follow-up or have exited the study earlier.

An independent data safety monitoring board (DSMB) will hold meetings after 5%, 25%, 50% and 75% of the total planned study population has completed Day 14 to evaluate partially blinded safety data for possible harmful effects of AGN-151607. More details regarding the policies, procedures, and composition of the DSMB, including precautions that will be employed to assure that inadvertent unblinding of parties does not occur; are described in the DSMB charter for this study. In addition, a separate SAP will be finalized before the first DSMB meeting.

13.0 Determination of Sample Size

A sample size of 100 randomized participants per treatment group will provide approximately 80% power to detect the treatment difference between each of the AGN-151607 doses (assumed equally effective) and placebo for the primary efficacy endpoint. The power calculations are based on the following assumptions:

- The expected incidence of early postoperative AF within 30 days post-surgery will be 47.8% in the placebo group and 27.8% in each of the AGN-151607 groups. This assumption is based on the results observed in the Pokushalov study (Pokushalov 2015) and the Duke University Medical Center clinical trial (Waldron et. al., 2019).
- Two-sided Mantel-Haenszel test statistic and a significance level of 0.05 for the test.

Calculations were performed using commercial software PASS 2008 (Hintze 2008). Assuming that approximately 10% in each intervention group will drop out early from the study, a total of approximately 330 participants will be randomly assigned to study intervention, in order to have approximately 300 participants complete all the efficacy assessments up to Day 60 visit.

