#### AGN-151607

suppression of AF and reduced vulnerability to provoked AF. No adverse safety findings were reported in these studies (Tsuboi 2002; Oh 2010; Oh 2011; Lo 2016).

Based on these findings, a clinical proof-of-concept study in 60 participants undergoing open-chest, coronary artery bypass grafting (CABG) cardiac surgery was conducted by an independent investigator (Pokushalov 2015). In this randomized, placebo-controlled, double-blind study, participants received epicardial injections of either botulinum toxin A (50 U of botulinum toxin A [incobotulinumtoxinA, Xeomin®] per fat pad; total of 200 U), or placebo, into 4 discrete fat pads. This study demonstrated that, over 30 days of follow-up, POAF occurred at a statistically significantly lower incidence in participants receiving intraoperative botulinum toxin type A injections (7% of participants) into epicardial fat pads compared with placebo injections (30% of participants). This study also reported that it was practical to administer botulinum toxin type A (total of 200 U) into the epicardial fat pads of these participants undergoing open-chest cardiac surgery and did not lead to safety problems, with follow-up through 3-years (Pokushalov 2015; Romanov 2019).

Following the Pokushalov publication, investigators at Duke University Medical Center conducted a clinical trial (Waldron 2019) in 130 participants undergoing open-chest, CABG and/or valve surgery. In this randomized, placebo-controlled, double-blind study, participants received epicardial injections of either botulinum toxin type A (50 U of botulinum toxin type A (onabotulinumtoxinA, [BOTOX®]) per fat pad; total of 250 U) or placebo into 5 discrete fat pads. This study demonstrated, over a mean follow-up of 6 days, that POAF occurred at a lower incidence in participants receiving intraoperative botulinum toxin type A injections (36.5% of participants) into epicardial fat pads compared with placebo injections (47.8% of participants). In addition, this study demonstrated that injections of a total of 250 U of botulinum toxin type A (50 U per fat pad) were safe and tolerable, with no increases in adverse events (AEs) or serious adverse events (SAEs) (Waldron 2019).

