# 9. Statistical Considerations

# 9.1. Statistical Hypotheses

In general, continuous variables will be summarized by descriptive statistics and will include sample size, mean, standard deviation, median, minimum, and maximum. Nominal variables will be summarized by frequency and percentage. Continuous variables will be analyzed using 2-sample t-test or analysis of variance (ANOVA) techniques for comparisons between treatment groups, and paired t-tests for within-group comparisons. Ordinal variables will be analyzed using Wilcoxon rank-sum or Cochran-Mantel-Haenszel (CMH) tests for pairwise comparisons between groups, and Wilcoxon signed-rank tests for within-group comparisons. Time-to-event data will be analyzed using Cox proportional hazards models or the Kaplan-Meier nonparametric model. Nominal variables will be analyzed using Pearson's chi-square test or, if 25% or more of the cells have expected counts less than 5, Fisher's exact test.

The analyses will include 3 treatment groups: Placebo, 125 U, and 250 U of AGN-151607. Each dose level of AGN-151607 (125 U and 250 U) will be separately compared to placebo. All treatment comparisons will be made at the  $\alpha = 0.05$  level (2-sided). To control for multiplicity in comparing 2 doses of AGN-151607 with placebo, the primary efficacy variable will be tested sequentially by first comparing the high dose to placebo. The low dose will be compared to placebo only if the comparison to the high dose is found to be statistically significant. Details regarding adjustment for multiple comparisons for other efficacy variables will be discussed in the SAP.

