# 9.2. Sample Size Determination

A sample size of 100 randomized participants per intervention group will provide approximately 80% power to detect the treatment difference between each of the AGN-151607 doses (assumed equally effective) and placebo for the primary efficacy endpoint. The power calculations are based on the following assumptions:

- The expected incidence of early postoperative AF within 30 days post-surgery will be 47.8% in the placebo group and 27.8% in each of the AGN-151607 groups. This assumption is based on the results observed in the Pokushalov study (Pokushalov 2015) and the Duke University Medical Center clinical trial discussed in Section 2 (Waldron 2019).
- Two-sided Mantel-Haenszel test statistic and a significance level of 0.05 for the test.

Calculations will be performed using commercial software PASS 2008 (Hintze 2008).

Assuming that approximately 10% in each intervention group will drop out early from the study, a total of approximately 330 participants will be randomly assigned to study intervention, in order to have approximately 300 participants complete all the efficacy assessments up to Day 60 visit.

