4.0 Introduction

This statistical analysis plan (SAP) provides a detailed elaboration of the statistical analyses of the efficacy and safety data as specified in the final protocol of Study 1925-201-008 (amendment 1 version dated 25 September 2020). Specifications of tables, figures, and data listings are contained in a separate document.

This is a phase 2, multi-center, randomized, double-blind, placebo-controlled, dose-ranging study in patients 55-90 years of age who are scheduled to undergo open-chest cardiac surgery.

The length of this study will be 367 days, not including the screening visit, which may occur up to 28 days before the first study day (randomization). Signed informed consent from the participant will be obtained before any study-related procedures are begun. Patients meeting the inclusion/exclusion criteria will be randomized (1:1:1 ratio) to one of three treatment arms at the end of the screening period. Primary and secondary efficacy assessments will be assessed for 30 days post-surgery. Additional efficacy and exploratory assessments will be assessed through Day 367 post-surgery. All participants will be followed through Day 367 for safety assessments. Every attempt will be made for participants who prematurely discontinue from the study, regardless of cause, to be seen for a final evaluation.

The study schema is presented below.

D = study day; TC = telephone call; U = units; V = Visit

a Hospital discharge could take more than 6 days.

The schedule of evaluations is presented in the Table 4–1 below.

Page 7

Table 4–1Schedule of Evaluations: Study 1925-201-008

Study Period	Screening ^a	Days 1 to 60						Day 61 through Day 360								
Visit Number	V1	V2	V3	V4 ^b	V5 ^b	V6 ^b	V7 ^b	TC1	V8	V9	V10	V11	V12	V13	TC2	Early
Day Number	(up to 28 days)	D1	D2	D3	D4	D5	D6	D14	D30	D60	D90	D180	D270	D360	D367 ^d	Disc
Visit Windows	-	-	-	-	-	-	-	± 3d	± 3d	± 3d	± 7d	± 7d	± 7d	± 7d	V13 + 7d (+ 7d)	-
Informed consent	Х															
Inclusion and exclusion criteria	Xe	Х														
Demography	Х															
Physical examination	Х								Х					Xf		Х
Medical history	X															
Urine pregnancy test (for women of childbearing potential) ^{e,g}	Х	x														
Laboratory assessments ^{e,h}	Х	Х					Х		Х	Xi	Xi			Xi		Х
Sample collection for biomarker assessment ^e		Х	х	Х	Х											
12-lead ECG ^j	Х	Х	Х	Х	Х	Х	Х		Х	Xk	Xk	Xk	Xk	Xk		Х
ECG patch		Х	Х	Х	Х	Х	Х	Х	X ¹	X ^m	Х					
Vital signs ^{e,n}	Х	Х	Х	Х	Х	Х	Х		Х	Х	Х	Х	Х	Х		Х

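### The roughly 80% power stated for each dose is single-comparison power; under the fixed sequence, 125 U has about 69% (74% uncorrected) at 100 per group

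*SAP*

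**What the plan says.** SAP 13.0 states that 100 per group "will provide approximately 80% power to detect the treatment difference between each of the AGN-151607 doses (assumed equally effective) and placebo" on the primary endpoint, and Protocol 9.2 makes the same statement. The stated inputs are rates of "47.8% in the placebo group and 27.8% in each of the AGN-151607 groups" and a "Two-sided Mantel-Haenszel test statistic and a significance level of 0.05 for the test". Allocation is equal: patients "will be randomized (1:1:1 ratio) to one of three treatment arms" (SAP 4.0).

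The testing order is given elsewhere. Protocol 9.1 tests 250 U against placebo first, and then: "The low dose will be compared to placebo only if the comparison to the high dose is found to be statistically significant". SAP 10.0 repeats the rule, with each comparison at two-sided 0.05. Neither sample-size section refers to this rule or gives a power for 125 U under it.

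**The concern.** The sample-size sections give one figure for both doses, but the testing plan treats them differently. For 250 U, success needs one significant comparison. For 125 U, it needs two: its own and the 250 U comparison before it. The probability of two successes cannot exceed the probability of either one, so a figure that is right for 250 U is too high as the chance of a formal conclusion on 125 U.

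This matters because the trial is dose-ranging. Protocol 4.3 includes the lower dose to learn whether it performs similarly to the higher one, and SAP 12.0 uses the Day 60 analysis, which is also the primary analysis, to plan later studies. A planner reading these sections would put the risk of ending without a formal 125 U claim at about one in five, even if both doses work exactly as assumed. Under the stated sequence that risk is larger.

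**Working it through.** **Inputs.** Placebo rate p0 = 0.478, rate on each dose p1 = 0.278, n = 100 per group, two-sided alpha 0.05 (Protocol 9.2, SAP 13.0); 1:1:1 allocation (SAP 4.0); fixed sequence with 250 U first (Protocol 9.1, SAP 10.0).

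**Step 1: reproduce the 80%.**

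- Standard error under the null: mean rate 0.378, so sqrt(2 × 0.378 × 0.622 / 100) = 0.0686.
- Standard error under the alternative: sqrt((0.478 × 0.522 + 0.278 × 0.722) / 100) = sqrt(0.4502 / 100) = 0.0671.
- Uncorrected: (0.20 − 1.96 × 0.0686) / 0.0671 = 0.978, giving power 83.6%.
- Continuity-corrected, subtracting 1/n = 0.01: (0.20 − 0.01 − 1.96 × 0.0686) / 0.0671 = 0.829, giving power 79.6%.

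The corrected version reproduces the plan's figure. It is the power of one dose-versus-placebo comparison, with no condition attached.

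**Step 2: power for 125 U under the sequence.** This is the probability that both comparisons are significant. They share the placebo arm, so the two statistics are correlated: p0(1 − p0) / [p0(1 − p0) + p1(1 − p1)] = 0.2495 / 0.4502 = 0.554. The bivariate normal probability that both are significant is 68.9% (corrected) or 74.3% (uncorrected).

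**Step 3: exact check.** Given the placebo count x0, the two dose arms are independent and have the same rate, so

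- power for one comparison = Σ P(x0) × P(reject | x0)
- power for both = Σ P(x0) × P(reject | x0)²

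with rejection by the unstratified Mantel-Haenszel chi-square in favour of the active dose:

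| n per group | Method | One comparison | Both (125 U claim) | 125 U given 250 U success |
|---|---|---|---|---|
| 100 | corrected | 79.7% | 68.6% | 68.6 / 79.7 = 86% |
| 100 | uncorrected | 83.6% | 74.0% | 74.0 / 83.6 = 89% |
| 110 | corrected | 83.5% | 73.5% | 73.5 / 83.5 = 88% |
| 110 | uncorrected | 86.6% | 78.0% | 78.0 / 86.6 = 90% |

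A simulation of the four-stratum CMH test at 100 per group, with assumed stratum shares and either equal or differing stratum risks, gave 69% corrected and 74% to 75% uncorrected. Stratification does not change the picture.

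**Step 4: where the loss comes from.** At 100 per group the gap is 79.7 − 68.6 = 11.1 points (corrected) or 83.6 − 74.0 = 9.6 points (uncorrected). It is the probability that the 125 U comparison would have been significant but is never formally made because 250 U was not.

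**The case against.** The strongest reply is that the sample-size sections describe a comparison of each dose with placebo by one test at 0.05. That is ordinary pairwise power, it is computed correctly, and the gate is disclosed in Protocol 9.1 and SAP 10.0. This stands in part. A reader might infer that the 80% is an arithmetic error, but it is not: Step 1 reproduces it. What is missing is the statement that it is single-comparison power, and the figure for 125 U under the planned sequence.

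A second reply is that 100 per group is pessimistic. About 330 are randomized, and the primary analysis uses the mITT population (SAP 6.1), which needs only treatment and one post-dose ePatch ECG by Day 30, whereas the 10% dropout allowance runs to Day 60. SAP 10.1 also mentions no continuity correction for the CMH test. This stands as a reason to show a range. With all 110 analysed and no correction, power for 125 U reaches 78%, close to 80%. But both sections attach their claim to 100 per group, and the method that reproduces the claim gives 69% there.

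Two stronger readings are tempting and are not supported:

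- A reader might infer that a non-significant formal test of 125 U would be over-read because its power is low. That test is made only after 250 U succeeds, and power is then about 86% to 89%. SAP 10.1 also presents effect estimates and confidence intervals for each dose. The weak point is that 125 U may go untested.
- A reader might infer that the 20-point effect misstates the two cited trials. Protocol Section 2 reports 30% versus 7% in one, a difference of 23 points, and "36.5% of participants) into epicardial fat pads compared with placebo injections (47.8% of participants" in the other, a difference of 11.3. Twenty points lies between them, and neither document claims a pooled mean. Power at smaller effects would be an optional addition.

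**Conclusion.** The point holds as a misattributed figure. About 80% is right for 250 U. For 125 U at 100 per group, the power under the planned sequence is about 69% by the method that reproduces 80%, or about 74% uncorrected, where each comparison has about 84%. The shortfall against single-comparison power by the same method is about 10 to 11 points. If all 110 randomized per group were analysed, power for 125 U would be about 74% to 78%.

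These figures rest on the plan's own rates, equal effectiveness of the two doses, equal group sizes and a shared placebo arm. If 125 U were less effective than 250 U, its power would be lower. Type I error, the 250 U test and the estimates are unaffected.

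**What to change.** In Protocol 9.2 and SAP 13.0, label the 80% as the power of a single comparison (250 U versus placebo). Add the power for 125 U under the testing sequence, computed by the same method: either 80% with 69% (continuity-corrected) or 84% with 74% (uncorrected). Do not pair a corrected figure for one dose with an uncorrected figure for the other. State the number per group to which the figures apply; if 110 is also shown, the pairs are 83.5% with 73.5%, or 86.6% with 78.0%.

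The cost is a sentence or two in each section and a less favourable figure for the lower dose. Sample size, alpha and testing order do not change.

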14.0 Statistical Software

Statistical analyses will be performed using version 9.2 (or newer) of SAS on a Linux operating system.

15.0 Data Handling Conventions

15.1 Visit Time Windows

Table 15–1 presents the visits assigned for safety analyses and the corresponding range of treatment days (window) during which an actual visit may occur. Unless otherwise specified, efficacy parameters collected by visit (e.g., Quality of Life Outcomes) will use the same windows during which an actual visit may occur. All analyzable ePatch data collected from ePatches with a start date within the visit window will be included in the analysis for the derived visit for Days 60, 90, 180, 270, and 360.

Scheduled Visit	Study Day ^a	Time Window (Study Day Range)
Baseline	1	1
Day 2	2	2
Day 3	3	3
Day 4	4	4
Day 5	5	5
Day 6	6	[6, 10]
Day 14	14	[11, 21]
Day 30	30	[22, 45]
Day 60	60	[46, 75]
Day 90	90	[76, 135]
Day 180	180	[136, 225]
Day 270	270	[226, 315]
Day 360	360	> 315 days

Table 15–1Analysis Visit Windows

a Relative to the date of the study treatment. Day 1 = the date of the study treatment.

If the assessment date (if the assessment date is unavailable, use visit date instead) is on or after the date of the study treatment, the study day is calculated by assessment date – date of the study treatment + 1. If the assessment date is before the date of the study treatment, the study day is calculated by assessment date – date of the study treatment. Therefore, a negative day indicates a day before the start of the study treatment.

If a subject has 2 or more visits within the same window, the last visit with a non-missing value will be used for analysis. All postbaseline assessments will be considered for PCS categorization. All assessments will be included in respective listings.

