# 8. Study Assessments and Procedures

- Study procedures and their timing are summarized in the SoA (Section 1.3).
- Visits 4, 5, 6, and 7 are optional and are only required if the participant is still hospitalized. Participants may remain in the hospital beyond Day 6, based on the recovery from surgery. The study visit procedures will have to be performed each day until discharge.
- Protocol waivers or exemptions are not allowed.
- Immediate safety concerns should be discussed with the sponsor immediately upon occurrence or awareness to determine if the participant should continue in the study.
- Adherence to the study design requirements, including those specified in the SoA, is essential and required for study conduct.
- All screening evaluations must be completed and reviewed to confirm that potential participants meet all eligibility criteria.
- Study visits after the index surgery may be conducted at the participant's home or other designated location in accordance with local ethics and/or IRB regulations, as well as with sponsor approval.
- Procedures conducted as part of the participant's routine clinical management (eg, chest X-ray or echocardiography) and obtained before signing of the ICF may be utilized for screening or baseline purposes provided the procedure met the protocol-specified criteria and were performed within the time frame defined in the SoA. However, testing of blood samples (including during unscheduled visits or samples for which local laboratory values are already available) should be conducted by the central laboratory.
- Local laboratory results are required only in the event that the central laboratory results are not available in time for either study intervention administration and/or response evaluation. Local laboratory results collected at the screening visit can be used to determine participant's eligibility if central laboratory results are not available. If a local sample is required, it is important that the sample for central analysis is obtained at the same time. Additionally, if the local laboratory results are used to make either a study intervention decision or response evaluation, the results must be entered into the eCRF.

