# 8.2.4. Clinical Safety Laboratory Assessments

- See Appendix 2, Section 10.2, for the list of clinical laboratory tests to be performed and the SoA for the timing and frequency.
  - The investigator must review the laboratory report, document this review, and record any clinically relevant changes occurring during the study in the AE section of the eCRF. The laboratory reports must be filed with the source documents. Clinically significant abnormal laboratory findings are those which are not associated with the underlying disease, unless judged by the investigator to be more severe than expected for the participant's condition.
- All laboratory tests with values considered clinically significant during participation in the study should be repeated until the values return to normal or baseline or are no longer considered clinically significant by the investigator.
  - If such values do not return to normal/baseline within a period of time judged reasonable by the investigator, the etiology should be identified and the sponsor notified.
  - All protocol-required laboratory assessments, as defined in Appendix 2, Section 10.2, must be conducted in accordance with the laboratory manual and the SoA.
  - If laboratory values from non-protocol specified laboratory assessments performed at the institution's local laboratory require a change in participant management or are considered clinically significant by the investigator (eg, SAE or AE or dose modification), then the results must be recorded in the eCRF.

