11.2 Clinical Laboratory Parameters

Descriptive statistics for clinical laboratory values (in SI units) and changes from the baseline values at each assessment time point will be presented by visit and treatment group for all continuous laboratory parameters. Categorical laboratory parameters will be presented in listings. The laboratory parameters are:

Hematology: Basophils absolute cell count, eosinophils absolute cell count, hematocrit, hemoglobin, lymphocytes absolute cell count, monocytes absolute cell count, neutrophil absolute cell count, mean corpuscular hemoglobin (MCH), mean corpuscular hemoglobin concentration (MCHC), mean corpuscular volume (MCV), platelet count, percentage reticulocytes, red blood cell (RBC) count, and white blood cell (WBC) count.

Chemistry:	Albumin, alanine aminotransferase (ALT), alkaline phosphatase, aspartate aminotransferase (AST), direct bilirubin, indirect bilirubin, total bilirubin, blood urea nitrogen (BUN), calcium, chloride, total cholesterol, creatinine, estimated glomerular filtration rate (eGFR), glucose non-fasting, triglycerides, HDL, LDL, Hemoglobin A1c, potassium, total protein, and sodium.
Urinalysis:	Bilirubin, blood, glucose, ketones, leukocyte esterase, nitrite, pH, protein, specific gravity, urobilinogen, and microscopic examination (if blood or protein is abnormal)
Coagulation:	Prothrombin time (PT), activated partial thromboplastin time (aPTT), and thrombin time (TT).

Clinical laboratory test values will be considered potentially clinically significant (PCS) if they meet either the lower-limit or higher-limit PCS criteria listed in Table 11–2. The number and percentage of participants who have PCS postbaseline clinical laboratory values will be tabulated by treatment group at each assessment. The percentages will be calculated relative to the number of participants with available non-PCS baseline values and at least 1 postbaseline assessment. The numerator will be the total number of participants with available non-PCS baseline values and at least 1 PCS postbaseline value. A supportive listing of participants with PCS postbaseline values will be provided, including the PID number, baseline and all postbaseline (including non-PCS) values.

Shift tables from baseline to each post-baseline visit for clinical laboratory parameters will be presented by treatment group for the following categories: low, normal, and high, which are provided by lab vendor.

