15.2 Repeated or Unscheduled Assessments of Safety Parameters

If a patient has repeated assessments before the start of the study treatment, the results from the last non-missing assessment made prior to the start of the study treatment will be used as baseline. If end-of-study assessments are repeated or if unscheduled visits occur, the last non-missing postbaseline assessment will be used as the end-of-study assessment for generating summary statistics. However, all postbaseline assessments will be used for PCS value determinations, and all assessments will be presented in the data listings.

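### SAP 15.1 takes the last value in each window, so a repeat laboratory value, often a recovered one, can replace the scheduled value in by-visit mean changes and shift tables

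*SAP*

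**What the plan says.** **Value selection.** SAP 15.1, on the windows in Table 15–1: "If a subject has 2 or more visits within the same window, the last visit with a non-missing value will be used for analysis". It expresses no preference for the scheduled visit or for the value nearest the target day. The windows that hold scheduled follow-up laboratory samples are Days 22–45 (Day 30), 46–75 (Day 60), 76–135 (Day 90) and everything after Day 315 (Day 360).

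**Repeat testing.** Protocol 8.2.4 says that laboratory tests with values considered clinically significant "should be repeated until the values return to normal or baseline or are no longer considered clinically significant by the investigator". Protocol Section 8 adds that "testing of blood samples (including during unscheduled visits or samples for which local laboratory values are already available) should be conducted by the central laboratory", so repeats can arrive in the same central dataset as scheduled samples.

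**Outputs.** SAP 11.2: "Descriptive statistics for clinical laboratory values (in SI units) and changes from the baseline values at each assessment time point will be presented by visit", split by arm. Also: "Shift tables from baseline to each post-baseline visit for clinical laboratory parameters will be presented by treatment group", using low, normal and high categories from the laboratory vendor.

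**Safeguards.** SAP 15.1: "All postbaseline assessments will be considered for PCS categorization". Sections 15.1 and 15.2 also put every assessment in the listings.

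**Unscheduled assessments.** SAP 15.2 covers baseline, PCS, listings and end of study. For end of study, "the last non-missing postbaseline assessment will be used as the end-of-study assessment for generating summary statistics". It does not say how an unscheduled repeat is treated in the by-visit summaries.

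**The concern.** The two rules interact. An abnormal value judged clinically significant is what generates a later value, and repeating stops when the value has recovered or no longer worries the investigator. Taking the last value in the window therefore makes the choice of analysed value depend on the outcome. A participant whose scheduled sample was unremarkable keeps that value, while a participant whose sample was abnormal may be represented by a later one.

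If a dose caused a transient laboratory effect around a scheduled visit, the by-visit means and shift tables would understate it most in the arm where it occurred. Those displays are supposed to describe the state at the visit, and a reader of the tables could not tell that some Day 30 entries were follow-up values.

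The same rule reaches the quality-of-life scores, because SAP 15.1 applies the windows to efficacy parameters collected by visit. Questionnaires are also completed at early discontinuation, unless withdrawal is after Day 180. An exit questionnaire on Day 130 falls in the Day 90 window and replaces an existing Day 90 score in the repeated-measures model of SAP 10.4.2. This is a smaller, exploratory matter, and no retest-until-recovery rule drives it.

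**Working it through.** The plan gives no figure on this point to reproduce. The check traces the rule through the windows and then shows how the result depends on quantities the documents do not give.

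**1. Room for a repeat in the same window.** Inputs are the upper window limits in SAP Table 15–1 and the visit windows in the Schedule of Activities. Days left = upper limit − day of the scheduled visit.

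| Visit | SAP window | Protocol visit window | Days left after nominal day | Range over the visit window |
|---|---|---|---|---|
| Day 30 | 22–45 | ±3 | 45 − 30 = 15 | 12 to 18 |
| Day 60 | 46–75 | ±3 | 75 − 60 = 15 | 12 to 18 |
| Day 90 | 76–135 | ±7 | 135 − 90 = 45 | 38 to 52 |
| Day 360 | > 315 | ±7 | no upper limit | no upper limit |

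The Day 6 window (6–10) leaves 4 days. Days 2 to 5 have one-day windows, so a later repeat of a discharge sample taken on Days 3 to 5 replaces nothing from that day.

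**2. What each output shows.** Take an illustrative participant with an abnormal Day 30 value judged clinically significant and a normal repeat on Day 40.
- Shift table and mean change at Day 30: the Day 40 value is used, so the participant appears normal.
- PCS table: the Day 30 value counts if it passes a Table 11–2 limit. For creatinine the limit is above 1.3 × ULN (upper limit of normal), so a value of 1.5 × ULN is kept and a value of 1.2 × ULN never enters.
- Parameters without a PCS limit: Table 11–2 has none for PT, aPTT, TT, eGFR, HbA1c, HDL, LDL, direct and indirect bilirubin, lymphocytes, monocytes, eosinophils, reticulocytes and the red cell indices. For these, the by-visit statistics and shift tables are the main laboratory tabulation.
- Adverse event tables and listings: the abnormal value is available there if recorded as Protocol 8.2.4 and Appendix 3 require.

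**3. Size in the shift table.** Let q be the share abnormal at the scheduled visit, and r the share of those with a recovered (in-range) repeat in the same window. Both are assumptions.

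Apparent abnormal share = q(1 − r)

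With q = 12% on drug and 5% on placebo, and the same r in both arms, the apparent difference is (12 − 5)(1 − r) = 7(1 − r) points:

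| r | Apparent difference (points) |
|---|---|
| 10% | 7 × 0.9 = 6.3 |
| 20% | 7 × 0.8 = 5.6 |
| 50% | 7 × 0.5 = 3.5 |
| 90% | 7 × 0.1 = 0.7 |

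**4. Size in the mean change.** If abnormal values exceed the recovered ones by an assumed 2 SD, an arm's mean is pulled back by 2qr SD. At q = 10% and r = 50% this is 2 × 0.10 × 0.50 = 0.1 SD.

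**The case against.** **The signal survives elsewhere.** A reader might infer that PCS categorisation is the only protection, so that a transient effect disappears from the safety results. The documents do not support that. Protocol 8.2.4 sends clinically relevant laboratory changes to the adverse event page, and Appendix 3 makes clinically significant results adverse events unless they belong to the underlying disease. Retesting is triggered by much the same judgement, so a value that is repeated will generally also be recordable as an adverse event and tabulated by arm under SAP 11.1. Listings hold every value. This objection stands, and it confines the problem to two descriptive displays.

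**Most abnormal values may never be repeated.** The shift table uses vendor ranges, whereas Protocol 8.2.4 repeats only values judged clinically significant. It also leaves out those associated with the underlying disease unless they are worse than expected. After cardiac surgery many out-of-range values may need no repeat. It is tempting to assume that most abnormal values are repeated and normal within the window, but no figure in the documents supports a high r, and low values must be shown as well. This stands.

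**The last value need not be normal.** Repeating may also stop at baseline or when the value is no longer considered clinically significant, so the last value can still be out of range and still show as a shift. Nor do the documents show that repeats usually fall in the same window; they show only that they can. Both points stand.

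**The rule says visits.** SAP 15.1 does not say that an unscheduled repeat counts as a visit. Nothing excludes it, however, and both SAP 15.2 and Protocol Section 8 speak of unscheduled visits. This is an ambiguity to settle and does not protect the tables.

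**The rule is prespecified, common to all arms, and feeds no laboratory test.** True, but a common rule still attenuates a difference when abnormal values, and hence repeats, are more frequent in one arm.

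**Conclusion.** The concern holds in a limited form. As written, the plan allows a later, outcome-selected value to stand in for the scheduled one in the by-visit laboratory mean changes and shift tables, and nothing in SAP 15.2 prevents it. With equal r in the arms, the shift-table effect is to understate abnormality and pull an arm difference toward zero.

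The practical gap is narrower than the whole safety assessment. It concerns parameters without a PCS limit, and values outside the normal range that do not reach one. Among the planned laboratory tables, only the shift tables show the latter as high or low.

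The size is unknown. The 7-point difference and the range from 6.3 to 0.7 points are illustrations that rest on assumed q and r, with r equal in both arms. Equal r is plausible because investigators stay blinded, but the documents do not establish it.

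The quality-of-life consequence is real but minor: it needs an exit after a scheduled questionnaire and inside the same window.

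**What to change.** In SAP 15.1, replace the last-visit rule with the following:

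- By-visit summaries use the value from the scheduled visit. If that is missing, they use the non-missing value in the window closest to the target day, and the earlier one on ties.
- Unscheduled repeats otherwise stay out of by-visit summaries. They continue to count for PCS and to appear in listings.
- An early-discontinuation questionnaire score is used only when the scheduled score in that window is missing.

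In SAP 11.2, add a shift from baseline to the worst postbaseline value, using all assessments. Where both directions matter, show the lowest and the highest separately. This gives parameters without PCS limits a table that keeps transient abnormalities.

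The end-of-study rule in SAP 15.2 can stay: SAP 11.2 specifies by-visit laboratory outputs, and changing 15.2 is not shown to alter any of them.

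The cost is SAP wording, minor programming and one additional shift table. It needs no new data and leaves the protocol's retesting rule as it is.
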